Protein restriction is a basic but important life intervention to improve the prognosis of DKD patients. How to calculate DPI in a simple and effective way to overcome the complexities and errors of existing methods attracts our attentions. In this study, we hypothesize sUCR can be applied to evaluate of protein intake during the follow-up periods and predict the survival in patients with DKD.

Object

To evaluate the prognostic value of sUCR in the progression of DKD.

Methods

This study is a multicenter, retrospective cohort study. We select patients diagnosed with DKD since January 2012. The present study is performed according to the principles of the Declaration of Helsinki and has been approved by the Ethics Committee of Guangdong Provincial People's Hospital.

Study population

We screen DKD patients aged 18-70 years with CKD stages 1-4. DKD was defined as those diagnosed by pathological biopsy, or those with eGFR <60 ml/min per 1.73 m², or presence of clinically detectable albuminuria over 3 months which is caused by diabetes. Patients who undergo infection, severe liver disease, malignant tumor, acute heart failure, gastrointestinal hemorrhage, pregnancy are excluded.

Data collection

At baseline and every medical visit, therapeutic relevant information will be collected. Data mainly include demographic characteristics (age, gender, place of residence, marriage status, education degree), lifestyle (smoking, drinking, exercise), clinical characteristics (body mass index, blood pressure, duration, history of CVD, complications, nutrition situation), laboratory indexes (serum creatinine, blood urea nitrogen, glycosylated hemoglobin, urinary albumin to creatinine ratio, 24-hour urinary albumin, 24-hour urine urea nitrogen, etc.). History of cardiovascular disease including coronary artery disease, congestive heart failure, stroke, and peripheral vascular disease were ascertained by self-report or doctor's diagnosis.

Outcomes

Patients are followed for survival until they reach the end of the study, whichever happen first, or are censored because they lose contact or the follow-up interval is less than one month. The outcomes are all-cause death, a composite of end-stage kidney disease (dialysis, transplantation, or a sustained estimated GFR of <15 ml per minute per 1.73 m², or increasing by 50% of the serum creatinine level from baseline. Evaluated GFR was calculated using Chronic Kidney Disease Epidemiology Collaboration (CKD-EPI) formula.

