Statistics

Data are presented as mean \pm SD for continuous variables and as a number (percentage) for categorical variables. According to mean sUCR and Δ sUCR (fluctuation of sUCR over time, meaning monthly rate of change), patients are divided into four groups. The relationship between baseline characteristics among the four groups was compared by using one-way analysis of variance test, Kruskal-Wallis test or Chi-squared test where appropriate. Survival rates are estimated using Kaplan Meier analysis, and the significance of differences are analyzed using the log-rank test. Cox proportional hazard regression analysis is used to assess the association between the clinical outcomes and mean sUCR and Δ sUCR. In multivariate analysis, we enter variables using a P value of <0.10 as the selection criterion or considered clinically significant. Hazard ratios (HRs) are presented with 95% CIs. All statistical analysis was performed with the use of SPSS (version 19.0, SPSS, Chicago, USA) and Prism 7.0 (GraphPad Software, San Diego, CA, USA). A two-tailed P value <0.05 was considered to be statistically significant.

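### ΔsUCR is a monthly rate of change with no fixed exposure window, so its error depends on a follow-up length that the outcome itself shortens; Cox results can be falsely significant, and a trend cannot speak to variability

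*Combined protocol and SAP*

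**What the plan says.** The Statistics section describes ΔsUCR as "fluctuation of sUCR over time, meaning monthly rate of change". From mean sUCR and ΔsUCR, "patients are divided into four groups"; no cut-points are given. The same section then states that "Cox proportional hazard regression analysis is used to assess the association between the clinical outcomes and mean sUCR and Δ sUCR".

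The values come from routine care. The Methods section says "This study is a multicenter, retrospective cohort study" and "We select patients diagnosed with DKD since January 2012", and under Data collection the information is gathered "At baseline and every medical visit". No visit schedule is set.

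The only floor on follow-up is under Outcomes, where one reason for censoring is that "the follow-up interval is less than one month". The wording is censoring, not exclusion, so it is unclear whether such patients contribute a ΔsUCR at all.

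The plan does not say how the rate is estimated, from how many values, over what period, or how that period relates to the start of time at risk.

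**The concern.** With no window stated, the natural reading is that each patient's rate of change uses every value from baseline to the end of that patient's follow-up. A slope from a few values over a short span has a large error; one from many values over years has a small error. Follow-up ends at an event, so patients with early events have the noisiest slopes and tend to fall in both tails of ΔsUCR by chance. Ordinary Cox regression treats ΔsUCR as a baseline quantity of equal quality in everyone. It can therefore find an association between ΔsUCR and outcome where none exists.

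ΔsUCR is one of only two exposures that the plan names. If it appears to be prognostic, a reader could not tell a real signal from the effect of short follow-up.

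A second, smaller point concerns the label. A rate of change measures direction over time and says nothing about swings around that direction.

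**Working it through.** The plan states no figure for this measure, so there is none to reproduce. The check is in four steps.

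**1. Error of one patient's slope.** Let s be the within-patient SD of sUCR at a visit, with independent visit errors. The least-squares slope has SE = s / √Σ(t − t̄)².

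- Two visits 1 month apart: s·√2 / 1 = 1.41 s per month.
- Visits at 0, 3, 6, 9 and 12 months: Σ = 36 + 9 + 0 + 9 + 36 = 90, so SE = s/√90 = 0.105 s per month.
- Quarterly visits over 60 months (21 values): Σ = 9 × 770 = 6930, so SE = s/√6930 = 0.012 s per month.

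The error differs by a factor of about 118 (1.414 / 0.0120) between the first case and the last. The documents allow a range this wide: January 2012 to the document date of June 2020 is about 101 months, and the floor is one month.

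**2. Signal against noise.** Let τ be the SD of true slopes between patients, in units of s per month. Reliability is τ²/(τ² + SE²). The documents do not give τ, so a range is assumed. With quarterly visits:

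| Follow-up | SE | τ = 0.05 | τ = 0.10 | τ = 0.20 |
|---|---|---|---|---|
| 6 months | 0.236 | 0.04 | 0.15 | 0.42 |
| 12 months | 0.105 | 0.18 | 0.47 | 0.78 |
| 60 months | 0.012 | 0.95 | 0.99 | 1.00 |

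At 6 months noise exceeds signal over this whole range. At 12 months the answer depends on τ.

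**3. Effect on the Cox analysis when sUCR is unrelated to outcome.** All inputs are assumptions: quarterly visits, events at about 12% a year, administrative follow-up of 12 to 72 months, at least two values per patient, and τ from 0 to 0.20. The table is from 100 runs of 800 patients.

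| τ | Hazard ratio, top quartile of absolute ΔsUCR | Share of ΔsUCR sum of squares from patients with 12 months or less |
|---|---|---|
| 0 | 9.2 | 80% |
| 0.05 | 3.1 | 66% |
| 0.10 | 2.0 | 45% |
| 0.20 | 1.5 | 24% |

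Patients with 12 months or less are only about 9% of the simulated cohort. A repeat simulation put the last hazard ratio at about 1.4. For the other ways of using ΔsUCR, over the same range of τ:

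- Continuous term: P < 0.05 in about 8% to 65% of runs, against a nominal 5%.
- Signed top quartile against the rest: hazard ratio about 2.5 at τ = 0, falling to about 1.1 at τ = 0.20.
- Signed median split: hazard ratio about 1.0, rejection in 3% to 9% of runs. With 100 runs, a true 5% has a standard error of √(0.05 × 0.95 / 100) = 2.2 percentage points, so this is close to nominal.

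With slopes from the first 12 months and outcomes counted only afterwards, the continuous test rejects in 3% to 5% of runs. In a separate run at τ = 0 (1500 patients, 40 runs), the signed and absolute median and quartile cuts then gave hazard ratios of 0.98 to 1.02 and rejection of 0% to 7.5%.

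**4. Trend against variability.** Take nine quarterly values alternating 20, 28, …, 20. The series is symmetric about its midpoint, so its slope is 0. The mean is 212/9 = 23.56, and the SD is √[(5 × 3.56² + 4 × 4.44²)/8] = 4.2. A perfectly stable patient also has slope 0, with SD 0. A smooth rise of 0.2 a month over the same 24 months has slope 0.2 and SD 1.6. By slope the steady riser ranks above the swinging patient; by SD the order is reversed.

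**The case against.** The strongest reply is that the plan does not describe the analysis that does the most harm. A monthly rate of change is signed, and four groups from two measures most naturally means a two-by-two split. If that split is at the medians, the simulation shows little average bias. This stands for the grouped comparison. It does not clear the plan, because the cut-points are not stated and the Cox model may use ΔsUCR as a continuous term, where the false-positive rate is inflated.

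It is also fair that no window is written at all. Use of all follow-up is the natural reading, not the text. Nor do the documents say that short follow-up usually reflects an early event; late entry and loss of contact shorten it too.

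Three stronger readings are tempting and are not supported.

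- A reader might take the hazard ratio of about 9 as the bias to expect. It needs a cut on the absolute value, which the plan does not state, and a cohort in which no patient has a true slope.
- A reader might suppose that noise only dilutes a continuous ΔsUCR towards no effect. The inflated rejection rate shows that dilution is not the only harm.
- A reader might conclude that the plan makes an invalid claim about fluctuation. The plan glosses the word at once as a rate of change, and its stated objective concerns the prognostic value of sUCR, not variability. That part is mainly a matter of labelling.

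**Conclusion.** The concern holds. As written, the plan allows the precision of an exposure to depend on the follow-up that the outcome ends, and then analyses that exposure without a window or landmark. This is more than a missing detail, because a team that followed the plan faithfully could report a false association.

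The size is uncertain. It rests on the assumed visit spacing, event rate, follow-up range and true-slope SD, none of which the documents give. Rejection rates also depend on the cohort size, which is not stated. The harm runs from almost none on average (signed median split) to large (quartile of absolute values when true slopes are absent), so no single hazard ratio should be quoted as the bias. Nor does the finding show that any association with ΔsUCR would be false; it shows that the planned analysis could not tell.

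The point about trend and variability needs no assumption, but it is answered by a change of name.

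**What to change.** - **Window.** Compute ΔsUCR, and the groups that use it, over one fixed, prespecified early window with a minimum number of values: for example the first 12 months and at least 3 values. Both numbers are choices, so repeat the analysis with other windows as sensitivity analyses.
- **Estimator.** State it. Slopes from a linear mixed model are preferable because noisy ones are shrunk, but fit the model only to values inside the window so that later data do not enter the exposure.
- **Time at risk.** Start it at the end of the window.
- **Short follow-up.** Say whether patients with less than one month are excluded or censored.
- **Cut-points.** State those that define the four groups, and whether the Cox model uses ΔsUCR as a continuous term or in categories.
- **Name.** Call ΔsUCR a trend. Add the within-window SD or coefficient of variation only if fluctuation is of interest.

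No new data are needed. The cost is more than wording, however. Events and patients lost within the window leave the ΔsUCR analysis; at the assumed 12% a year, a 12-month window would remove about 12% of patients through events alone. The results then apply to patients who are event-free at the end of the window. Patients with too few values also leave this analysis, but can stay in an analysis of mean sUCR alone.

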Project Name: The association between serum urea nitrogen to creatinine ratio and the survival in patients with DKD.

No.: v1.2 version Date: June 1, 2020

Study unit: Guangdong Provincial People's Hospital

Sponsor: Guangdong Provincial People's Hospital

Background

In 2013, the prevalence of adult diabetes in China was as high as 10.9%, with the number of patients exceeding 100 million. Diabetic kidney disease (DKD), as one of the main microvascular complications of diabetes, occurs in 20% ~ 40% of diabetes. Furthermore, Diabetes-related chronic kidney disease, the leading cause of chronic kidney disease, has become a serious public health problem and brought huge economic burden. How to realize the early prevention and treatment of DKD and improve its clinical outcomes raises our concerns.

Previous studies have shown that a low-protein diet (LPD) can retard renal function decline in patients with CKD mainly through the improvement of glomerular hyperfiltration/hyperfusion and tubule-interstitial damage, inflammation and fibrosis. The lower the baseline dietary protein intake (DPI), the slower the progression toward ESRD. Each 0.1 g/kg per day higher DPI at baseline was associated with a loss of kidney function that was faster by approximately 0.064 ml/min per year. In 2020, standards of medical care in diabetes of American diabetes Association (ADA) recommended for people with nondialysisdependent CKD to maintain DPI approximately 0.8 g/kg body weight per day. Previous studies provided some methods for dietary assessment such as 24-hour dietary recalls, food diaries and food frequency questionnaires, which exist limitations including:(1)reliance on patient's memory, compliance and communication ability; (2)reliance on interviewer's skills, comprehensiveness and prompts;(3)lack of ability to represent a longer period. Maroni formula, which tests 24-hour urine urea nitrogen, is a relatively objective and common method to evaluate protein intake, but can't be generalized due to its complexity and uncertainty. Joel D et.al found that serum urea nitrogen to creatinine ratio (sUCR) correlated closely with protein intake and knowledge of its relation to protein intake could be used to determine the degree of protein restriction. In our previous study, the mathematical model between sUCR and DPI was preliminarily established after modeling and verification, and has obtained the patent.

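### The cohort is described as multicenter, but the plan does not commit to recording centre or to using it in the log-rank or Cox analyses, so part of an apparent sUCR association could be between-centre

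*Combined protocol and SAP*

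**What the plan says.** The Methods section states: "This study is a multicenter, retrospective cohort study". The title block names one site, "Study unit: Guangdong Provincial People's Hospital", and no section gives the number or identity of the centres.

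Under Data collection, the demographic items are "demographic characteristics (age, gender, place of residence, marriage status, education degree"; place of residence is the nearest of them to a centre identifier. The laboratory items are "laboratory indexes (serum creatinine, blood urea nitrogen, glycosylated hemoglobin, urinary albumin to creatinine ratio, 24-hour urinary albumin, 24-hour urine urea nitrogen, etc". No hospital, laboratory or assay field is named, and no central measurement or harmonisation of creatinine is described. The list is introduced as the main items only, and its laboratory part is left open, so it is not exhaustive.

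Under Statistics, mean sUCR and its monthly change define the exposure: "patients are divided into four groups". The groups are compared as follows: "Survival rates are estimated using Kaplan Meier analysis, and the significance of differences are analyzed using the log-rank test". Then "Cox proportional hazard regression analysis is used to assess the association between the clinical outcomes and mean sUCR and Δ sUCR". For the multivariable model, "we enter variables using a P value of <0.10 as the selection criterion or considered clinically significant". Centre does not appear as a stratum, covariate, random effect or cluster in any of these steps.

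**The concern.** In a retrospective study over several hospitals, urea and creatinine presumably come from each hospital's own routine laboratory. Creatinine is the denominator of sUCR, so a proportional calibration difference shifts every sUCR value at that hospital and changes how its patients spread over the exposure groups. Outcome risk can differ by hospital too, through case-mix, completeness of follow-up and, for the renal outcome, local dialysis practice. Patients are not randomised, so nothing balances centre across sUCR groups.

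When centre is linked to both exposure and outcome, a pooled comparison mixes the within-hospital association, which is the one of interest, with a contrast between hospitals. The stated object is the prognostic value of sUCR. Without centre in the data or the analysis, a reader of the results could not separate the two. The bias does not shrink with sample size, so a larger cohort makes a spurious finding more likely.

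**Working it through.** **Is there a plan figure to reproduce?** No. The documents give no sample size, event count, effect size or number of centres. Every number below is an illustration under stated assumptions.

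**Illustration 1: Cox model on continuous sUCR.** Assumptions: 800 patients; four equal centres; true sUCR effect zero; two centres with mean sUCR higher by d within-centre SDs and event hazard multiplied by H; baseline hazard 0.06 per year; censoring uniform over 1 to 8 years; no covariates.

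Hand calculation:
- Variance of sUCR over all patients: V = 1 + d²/4.
- Spurious log hazard ratio per within-centre SD: b ≈ (d/2)(ln H/2)/V.
- Event probability at hazard λ: 1 − (e^(−λ) − e^(−8λ))/(7λ). This is 0.231 at 0.06, 0.278 at 0.075, 0.322 at 0.09 and 0.400 at 0.12.
- Expected events: D = 400 × (sum of the two event probabilities).
- z = b√(V·D); false-positive rate ≈ Φ(z − 1.96) + Φ(−z − 1.96).

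For d = 0.5 and H = 2: V = 1.0625; b = 0.25 × 0.3466/1.0625 = 0.0815, a hazard ratio of 1.085; D = 400 × 0.631 = 252; z = 0.0815 × √(1.0625 × 252) = 1.335; rate = Φ(−0.625) + Φ(−3.295) ≈ 0.27.

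| d (SD) | H | D | Spurious HR | Rate, by hand | Rate, simulated pooled |
|---|---|---|---|---|---|
| 0.25 | 1.25 | 204 | 1.014 | 5.4% | 5-6% |
| 0.25 | 1.5 | 221 | 1.025 | 6.6% | about 7% |
| 0.5 | 1.5 | 221 | 1.049 | 11.3% | 10-12% |
| 0.5 | 2.0 | 252 | 1.085 | 26.7% | 25-27% |

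The last column is the range over separate simulation runs, the largest with 2,000 replicates. One run of only 200 replicates gave about 5% in the second row; at that size the 95% simulation margin is ±1.96√(0.05 × 0.95/200) = ±3 percentage points, so the larger runs are preferred. Centre-stratified Cox gave hazard ratios of 0.99-1.00 and false positives of about 4-6% in every scenario, with a standard error about 1-4% larger.

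**Illustration 2: log-rank test on a median split.** Assumptions: two equal centres; log-normal sUCR with log-SD 0.30; baseline hazard 0.08 per year; five years of follow-up; true hazard ratio 1; 1,500 runs per cell. Creatinine reads 10% or 20% high at the higher-risk centre, a shift of ln(1.1)/0.30 = 0.32 SD or ln(1.2)/0.30 = 0.61 SD.

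| Creatinine shift | Centre HR | N = 300 | N = 600 | N = 1200 | Spurious HR |
|---|---|---|---|---|---|
| 10% | 1.5 | 5.5% | 6.1% | 8.9% | about 1.05 |
| 20% | 2.0 | 13.3% | 25.2% | 45.7% | 1.17-1.18 |

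With a shift alone or an outcome difference alone, the pooled test stayed at about 5% (3.9-5.5%). The stratified test was between 3.7% and 6.0% in every cell.

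**How far do patients move between groups?** With d = 0.5 and a pooled median cut midway between the two centre means, Φ(0.25) = 60% of patients at the shifted centres fall in the high half, against 40% elsewhere.

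**The case against.** The strongest reply is that the plan leaves room for centre. The data list is not exhaustive, and the covariate rule admits variables on clinical judgement without any P value. A reader might infer that centre is barred from the Cox model; the text does not say so. That part of the reply stands, but permission is not commitment: the choice would be made after the data are seen, and the rule does nothing for the log-rank test.

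Second, the multivariable Cox model can draw on age, blood pressure, cardiovascular history, HbA1c, creatinine and albuminuria, which would absorb part of any case-mix difference between hospitals. This also stands. A reader might infer that nothing in the plan touches this confounding, and that goes too far. The illustrations carry no covariates, so their centre hazard ratios must be read as what remains after adjustment, and the documents do not show residuals of 1.5 or 2.0.

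Third, the calibration mechanism is narrower than it may look. A constant proportional difference leaves the sign of a patient's monthly sUCR change intact and cancels from a 50% creatinine rise. It does not cancel from mean sUCR or from the eGFR threshold in the renal outcome. Dialysis practice does not define all-cause death.

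Fourth, hospitals may differ in sUCR because protein intake truly differs, and that is what sUCR is meant to reflect. This counts against grouping patients on within-centre values as the main analysis, since doing so discards real differences and any common threshold. It does not count against stratifying the tests.

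Last, one hospital may supply most or all patients. If so, the effect shrinks or vanishes, but the description of the design then needs correcting.

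**Conclusion.** The point holds as a gap worth closing, not as a demonstrated bias. That centre is not named in the data list or in any planned comparison can be read directly from the text. Harm needs two conditions together: hospitals that differ in sUCR level, and hospitals that differ in outcome risk after adjustment. Under the assumptions above, the false-positive rate goes from negligible inflation (5-7% at a 0.25 SD shift) to about 25% at a 0.5 SD shift with a centre hazard ratio of 2.0. The spurious effect in that worst case of the first illustration is about 1.08 per SD.

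A reader might infer that whole hospitals change group, or that a significant result could be entirely a hospital effect. The documents do not support either: they give no centre data, and even at 0.5 SD the split is 60% against 40%. Confidence is high about the omission and low about the size of any bias. Because the remedy is cheap, the plan should adopt it.

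**What to change.** 1. Reconcile the single study unit in the title block with the multicenter description in Methods, and state the number and identity of the centres. If there is only one, correct Methods and the point falls away.
2. Add study centre to the data list for each patient.
3. Stratify every log-rank test and Cox model by centre, whatever the P<0.10 screen shows, with very small centres pooled into one stratum.
4. Report the number of patients in each sUCR group by centre.
5. If sUCR cut-points defined within centre are wanted, keep them to a sensitivity analysis.

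The cost is one field that should already be known for each record, one stratification term per procedure, and one descriptive table. The statistical price is a small loss of precision, about 1-4% on the standard error in the illustration, and possibly more if many centres have few events.

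### ΔsUCR, a slope, is summarised by one constant Cox hazard ratio with no proportionality check, and the plan cannot show whether that single figure is valid

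*Combined protocol and SAP*

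**What the plan says.** The Statistics section of the combined protocol and SAP defines ΔsUCR as "fluctuation of sUCR over time, meaning monthly rate of change". Using mean sUCR and ΔsUCR, "patients are divided into four groups". For these groups, "Survival rates are estimated using Kaplan Meier analysis, and the significance of differences are analyzed using the log-rank test". For the exposures themselves, "Cox proportional hazard regression analysis is used to assess the association between the clinical outcomes and mean sUCR" and ΔsUCR, with hazard ratios and 95% confidence intervals.

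The section mentions no proportionality check, exposure-by-time term, time-updated covariate or period-specific hazard ratio. It does not say over what period mean sUCR and ΔsUCR are calculated, or whether they enter one model or two.

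Methods says "We select patients diagnosed with DKD since January 2012", and the document is dated 1 June 2020. No follow-up duration or closing date is given. The hypothesis, stated just before the Object section, is that sUCR can gauge protein intake over follow-up and predict survival. It gives no functional form for the hazard. Data collection provides for laboratory values at baseline and at every visit.

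**The concern.** A patient's slope says how far the sUCR level will have moved by a given time. If the hazard depends on the level, two patients with the same starting level and different slopes have almost the same risk at first and increasingly different risk later. A Cox model with a fixed ΔsUCR coefficient compresses this into one average, weighted by when events happen to occur. A cohort followed for longer would then report a larger hazard ratio for the same biology.

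If the comparison is made at a fixed mean over the whole follow-up, a steeper slope means a lower level early and a higher level late, so the two effects oppose each other. ΔsUCR is one of only two named exposures, and the plan has no step that would show the analyst that any of this had happened.

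**Working it through.** **Inputs.** The documents give no sample size, event count, target hazard ratio or spread of slopes, so there is no plan figure to reproduce. From January 2012 to 1 June 2020 is 8 + 5/12 = 8.4 years, the longest follow-up at the document date. All other inputs below are assumptions.

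**Algebra.** Let sUCR(t) = a + s·t and log-hazard = β·sUCR(t). The log hazard ratio per unit of slope is:

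- given baseline level a: β·t
- given the mean over a period of length T, which equals a + s·T/2: β·(t − T/2)

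The first grows and keeps its sign. The second changes sign at mid-period.

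**Closed form.** Take a hazard ratio of 1.5 per SD of level, a slope SD of one level-SD per 30 months, and T = 60 months. The hazard ratio per SD of slope is 1.5^(t/30) given baseline and 1.5^((t−30)/30) given the mean.

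| Month | 0 | 15 | 30 | 45 | 60 |
|---|---|---|---|---|---|
| Given baseline | 1.00 | 1.22 | 1.50 | 1.84 | 2.25 |
| Given 60-month mean | 0.67 | 0.82 | 1.00 | 1.22 | 1.50 |

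**What a constant-hazard-ratio fit reports.** Same inputs, 600 patients, 300 replicates, about 75 to 320 events:

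| Model for ΔsUCR | HR per SD | Rejection at 5% |
|---|---|---|
| Alone, slope uncorrelated with baseline | 1.39–1.51 | 94–100% |
| Alone, correlation with baseline −0.5 | 1.20 | 69% |
| Alone, correlation with baseline −0.7 | 1.11 | 26% |
| Alone, slope uncorrelated with follow-up mean | 0.96–0.99 | 6–14% |
| With fixed 60-month mean in the model | 0.95–1.03 | 4–19% |
| With each patient's own follow-up mean in the model | 1.00–1.15 | 5–25% |

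With β = 0 the fits rejected in 6–11% of replicates, so most of the last three rows is close to no power.

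**Exposure fixed in year 1, trend persisting.** The window mean is centred at 0.5 year, so the log hazard ratio per SD of slope is β·σ·(t − 0.5), where σ is the slope SD in level-SDs per year. For example, with β = ln 1.3 = 0.262 and σ = 0.15, t = 2 gives exp(0.262 × 0.15 × 1.5) = 1.06 and t = 6 gives exp(0.262 × 0.15 × 5.5) = 1.24. The simulated columns use base hazard 8% per year, loss 5% per year, staggered follow-up to 8.4 years, and 40 runs of 4,000. Early is the first two years after the window; late is after year 4.

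| HR per SD of level | σ | Formula, t = 2 | Formula, t = 6 | Simulated early | Simulated late | Single HR |
|---|---|---|---|---|---|---|
| 1.3 | 0.15 | 1.06 | 1.24 | 1.05 | 1.26 | 1.11 |
| 1.3 | 0.25 | 1.10 | 1.43 | 1.10 | 1.46 | 1.19 |
| 1.5 | 0.15 | 1.10 | 1.40 | 1.10 | 1.40 | 1.18 |
| 1.5 | 0.25 | 1.16 | 1.75 | 1.14 | 1.78 | 1.28 |

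A further set of runs gave 1.01–1.17 early, 1.22–1.61 late and 1.08–1.32 for the single value, so the pattern is stable but the exact figures are not.

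**Sensitivity.**

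- Follow-up length: with the full trend persisting, the single value was 1.04–1.15 with 3-year follow-up and 1.11–1.29 with 8.4-year follow-up.
- Half the trend persisting: 1.04–1.10 early, 1.11–1.37 late, single 1.07–1.16.
- No trend after the window: 1.02–1.05 in every period, which is proportional.
- Mean and slope over the whole follow-up: 0.99–1.04 for ΔsUCR modelled jointly with the mean, against 1.09–1.28 for ΔsUCR alone.

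**The case against.** The strongest reply is that the premise is brought in from outside. The documents state neither a hazard that depends on the current level nor a linear trend lasting years, and the Statistics section treats ΔsUCR as an exposure in its own right. If risk follows the slope, or the trend ends with the exposure window, one hazard ratio is adequate. This stands. A reader might infer that defining ΔsUCR as a rate of change is enough to make its hazard ratio vary; it is not.

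A reader might also infer that a real ΔsUCR effect will be reported as null. The documents do not support that either. Given baseline or early-window level, the effect keeps one direction and the single value is a non-null average. Near-null results need the follow-up mean held fixed, by joint adjustment or because slope happens to be unrelated to that mean; a strong negative correlation with baseline weakens the result part of the way. The plan names both exposures in one sentence, which makes a joint model plausible, but it does not state one. Even then the level effect is not lost, because it falls on the mean-sUCR coefficient.

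The reply that only a routine check is missing does not dispose of the point. The level-based reading is a natural one for this hypothesis, and under it a constant ΔsUCR hazard ratio is wrong by construction.

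**Conclusion.** The point holds in conditional form. The plan reports a constant hazard ratio for a slope over a potentially long follow-up and has no step to separate the case where that is valid from the case where it is not.

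Under the level-based reading with persisting trends and the assumed inputs, a single value of about 1.1 to 1.3 covers early values close to 1 and late values of roughly 1.2 to 1.8, and it depends on follow-up length. If ΔsUCR is adjusted for the whole-follow-up mean, it can appear to have a hazard ratio near 1.0. The error would then be a mistaken statement that ΔsUCR has no effect, not a loss of the sUCR signal.

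A reader might also infer that the group hazards must cross. In runs at a hazard ratio of 1.3 per SD, which were not repeated, the high-mean falling versus low-mean rising contrast went from 1.40 in years 0–2 to 1.06 after year 4 at σ = 0.15, with no crossing, and from 1.30 to 0.89 at σ = 0.25. Crossing therefore depends on a spread of slopes that the documents do not give. The size of the problem in this cohort cannot be derived from the plan. The change is worthwhile and inexpensive, but nothing here shows that the planned analysis will fail.

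**What to change.** In Statistics:

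1. Test proportionality of ΔsUCR, mean sUCR and each covariate, by a ΔsUCR × time term or scaled Schoenfeld residuals. Where it fails, report period-specific hazard ratios (for example 0–2, 2–4 and more than 4 years) in place of one constant value.
2. State whether mean sUCR and ΔsUCR enter the same model, and over what period each is calculated.
3. Add a Cox model with sUCR as a time-updated covariate, using the visit data already collected. If mean and slope cover the whole follow-up, they use measurements taken after the risk times being analysed, and a ΔsUCR × time term alone does not repair this. Under the level-based reading it would show first-half hazard ratios of 0.97–0.995 for rising sUCR, an apparent early benefit, and 1.03–1.18 in the second half. Take the updated value from a visit before the event, because creatinine is both the denominator of sUCR and part of the outcome definition.

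Restricted mean survival time beside the log-rank test is optional.

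The cost is SAP wording and a little extra analysis on existing data. Period-specific hazard ratios will have wider confidence intervals than one pooled value.
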